14.3 Efficacy Analysis

Efficacy analysis will be performed on the efficacy population as defined in Section 14.7.1. Efficacy endpoints include length/height AGV and length/height standard score (Z-score) at Week 52.

For a given interval [Date1, Date2], the AGV is defined as follows:

$$\text{AGV} = \frac{\text{Length/standing height at Day 2} - \text{Length/standing height at Day 1}}{\text{Interval Length (Days)}} \times 365.25$$

where the interval length in days is calculated as Date2 – Date1. AGV will be calculated for the following visits/intervals:

- Baseline: [Date of last length/height measurement in study 901 at least 6 months prior to screening visit in study 206, Date of Day 1]
- Week 13: [Date of Day 1, Date of Week 13]
- Week 26: [Date of Day 1, Date of Week 26]
- Week 39: [Date of Day 1, Date of Week 39]
- Week 52 (12-month): [Date of Day 1, Date of Week 52]

The baseline of the AGV is established in the natural history study of Study 111-901, based on the standing height measurements in the last 6 months prior to enrollment to Study 111-206. AGV will be summarized using descriptive statistics (mean, SD, median, minimum, and maximum). Results will be summarized by treatment group and cohort.

The measurement of length/standing height will be converted to age-and sex-appropriate standard score (SDS), also referred to as Z-score, by comparison with normal reference standards (not ACH). The Z-score will be summarized similarly to growth velocity.

Comparisons between treatment groups by cohort on these variables will be carried out where appropriate. Statistical comparisons will be considered descriptive. Additional details regarding efficacy analysis will be provided in the SAP.

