9 INVESTIGATIONAL PLAN

9.1 Overall Study Design and Plan

This is a Phase 2 randomized, double-blind, placebo-controlled clinical trial of BMN 111 in infants and younger children with a diagnosis of ACH.

Subjects age ≥ 3 months to < 60 months old who have documented ACH confirmed by genetic testing, at least a 6-month period of pretreatment growth assessment in Study 111-901 immediately before study entry and who meet the study eligibility criteria will participate. Eligible subjects ranging from 0 months to < 3 months old may enroll directly into 111-206 and have a minimum of 3 months of pre-treatment observation prior to commencing treatment.

Approximately 70 subjects will be enrolled at approximately 10-15 clinical centers worldwide.

The primary objectives of this study are to assess the safety and tolerability of daily SC BMN 111 administered to infants and young children with ACH, and evaluate the effect of BMN 111 on Z-scores. Subjects will be enrolled into 3 age cohorts based on age at study screening starting with the eldest population. Within Cohorts 1 and 2, subjects will be stratified by age:

- Cohort 1 – children aged ≥ 24 to < 60 months (n ≥ 30 total: 3 sentinel subjects who receive BMN 111, and at least 27 additional subjects randomized 1:1 to treatment or placebo control), stratified by age (≥ 24 to < 36 months and ≥ 36 months to < 60 months)
- Cohort 2 – children aged ≥ 6 to < 24 months (n ≥ 20 total: 3 sentinel subjects who receive BMN 111, and at least 17 additional subjects randomized 1:1 to treatment or placebo control), stratified by age (≥ 6 months to < 15 months and ≥ 15 months to < 24 months)
- Cohort 3 – children aged 0 to < 6 months (n ≥ 20 total: 3 sentinel subjects who receive BMN 111, and at least 20 additional subjects randomized 1:1 to treatment or placebo control). Treatment begins at ≥ 3 months to < 6 months after 3 months of observation.

If subjects who enroll in Cohort 3 are not able to begin treatment by < 6 months of age, they will continue in the pretreatment period for another 3 months before enrolling in Cohort 2 to fulfill the pretreatment requirement for Cohort 2.

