9.3.1 Inclusion Criteria

Individuals eligible to participate in this study must meet all of the following criteria:

1. Diagnosis of ACH, confirmed by genetic testing. If subjects had previous genetic testing, subjects must have a lab report from a certified laboratory with the study specific mutation documented.
2. Age 0 to < 60 months, at study entry (Day 1)
3. Cohort 1 and 2 subjects must have at least a 6-month period of pretreatment growth assessment in Study 111-901 immediately before study entry, and have one documented measurement of height/body length a minimum of 6 months (+/- 10 days) prior to the screening visit for 111-206. Cohort 3 subjects must have a minimum of 3 months of observation prior to treatment. This observational period can be obtained either (1) via prior enrollment in Study 111-901 or (2) via enrollment in this Study 111-206 for a minimum of 3 months of non-treatment observation prior to commencement of treatment.
4. Parent(s) or guardian(s) (and the subjects themselves, if required by local regulations or ethics committee) are willing and able to provide written, signed informed consent after the nature of the study has been explained and prior to performance of any research-related procedure
5. Willing and able to perform all study procedures as physically possible
6. Parent(s) or caregiver(s) are willing to administer daily injections to the subjects and complete the required training

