9.11.3 Secondary Efficacy Variables

The secondary efficacy endpoints include change from baseline in AGV (annualized to cm/yr), biomarker samples to evaluate the effect of BMN 111 on bone metabolism, and BMN 111 pharmacodynamic biomarkers.

Weight will be measured at Screening and at study visits as indicated on the Schedule of Events (Table 9.1.1 and [Table 9.1.2](#)).

Biomarkers may include but are not limited to assessment of changes in bone and collagen metabolism and BMN 111 bioactivity. BioMarin or designee will perform analysis, and samples may also be used for assay development.

Samples for blood and/or urine biomarkers will be collected at the time points presented in the Schedule of Events (Table 9.1.1 and [Table 9.1.2](#)). Refer to the Study Laboratory Manual for instructions regarding obtaining and shipping samples. The sample type will also be included in the Study Laboratory Manual.

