9.3.1 Inclusion Criteria

Individuals eligible to participate in this study must meet all of the following criteria:

1. Diagnosis of ACH, confirmed by genetic testing. If subjects had previous genetic testing, subjects must have a lab report from a certified laboratory with the study specific mutation documented.
2. Age 0 to < 60 months, at study entry (Day 1)
3. Cohort 1 and 2 subjects must have at least a 6-month period of pretreatment growth assessment in Study 111-901 immediately before study entry, and have one documented measurement of height/body length a minimum of 6 months (+/- 10 days) prior to the screening visit for 111-206. Cohort 3 subjects must have a minimum of 3 months of observation prior to treatment. This observational period can be obtained either (1) via prior enrollment in Study 111-901 or (2) via enrollment in this Study 111-206 for a minimum of 3 months of non-treatment observation prior to commencement of treatment.
4. Parent(s) or guardian(s) (and the subjects themselves, if required by local regulations or ethics committee) are willing and able to provide written, signed informed consent after the nature of the study has been explained and prior to performance of any research-related procedure
5. Willing and able to perform all study procedures as physically possible

6. Parent(s) or caregiver(s) are willing to administer daily injections to the subjects and complete the required training

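### Baseline AGV as defined in Section 14.3 cannot be computed for Cohort 3, because its start date falls before birth

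*Protocol*

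**What the plan says.** Section 14.3 defines AGV for a general interval and then lists the intervals to be used. The baseline interval is "Date of last length/height measurement in study 901 at least 6 months prior to screening visit in study 206, Date of Day 1". No cohort is exempted and no alternative is given. A later sentence in the same section says that the AGV baseline comes from Study 111-901, "based on the standing height measurements in the last 6 months prior to enrollment to Study 111-206".

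Section 9.1 sets the ages: "Subjects will be enrolled into 3 age cohorts based on age at study screening starting with the eldest population". Cohort 3 covers 0 to under 6 months, and "Treatment begins at ≥ 3 months to < 6 months after 3 months of observation". Inclusion criterion 3 in Section 9.3.1 adds that "Cohort 3 subjects must have a minimum of 3 months of observation prior to treatment". It allows that period to be spent in Study 111-901 or "via enrollment in this Study 111-206 for a minimum of 3 months of non-treatment observation prior to commencement of treatment". For Cohorts 1 and 2 the same criterion asks for a documented measurement "a minimum of 6 months (+/- 10 days) prior to the screening visit for 111-206".

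Section 9.11.3 names the change in AGV from baseline among the secondary efficacy endpoints. The synopsis plans to summarize AGV and its change by treatment group and by cohort, which includes Cohort 3.

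**The concern.** The baseline rule fits children who have spent 6 months or more in the natural history study. It does not fit infants who enter before 6 months of age with 3 months of observation. Applied literally, it yields no baseline velocity, and so no change in AGV, for any child in Cohort 3. Section 14.1.2 rules out imputation unless it is specified for the efficacy analyses, so the protocol itself does not fill the gap.

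At stake is one secondary endpoint in the youngest cohort. An analyst must either report nothing for that cohort or depart from the stated interval. Section 14.1.1 plans an interim analysis to support filing, so the choice could be made after data have been seen. Two smaller mismatches affect Cohorts 1 and 2: a 10-day difference between eligibility and the AGV rule, and a second baseline sentence worded differently from the first.

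**Working it through.** The protocol made no formal sample size calculation and gives no figure for this endpoint, so there is nothing to reproduce. The check is date arithmetic.

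**Inputs**
- Start of the baseline interval: at least 6 months before the 111-206 screening visit, measured in 111-901 (Section 14.3).
- Cohort 3: under 6 months old at screening; treatment starts at 3 to under 6 months of age (Section 9.1).
- Screening for treatment: Day -30 to Day -1 (Table 9.1.1).
- Minimum randomized numbers: 27, 17 and 17 for Cohorts 1, 2 and 3 (synopsis and amended Section 9.1).
- Conversion: 6 months = 6 × 365.25/12 = 182.6 days; 3 months = 91.3 days.

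**Cohort 3**
- Age at the latest qualifying measurement = age at screening − 182.6 days.
- Age at screening is below 182.6 days, so the result is below 0, before birth.
- Since Day 1 must also come before 6 months of age, the bound is tighter. With screening on Day -1, age at screening is below 181.6 days and the result is below −1 day. With screening on Day -30, age at screening is below 152.6 days and the result is below −30 days.
- If the relevant screening visit is instead the one that opens the observation period, for infants under 3 months, the result is below 91.3 − 182.6 = −91.3 days.
- Children observed only inside 111-206 have no 111-901 measurement of any date.

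The baseline is therefore undefined for every child in Cohort 3.

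**Share of the efficacy population**
- Section 14.7.1 limits this population to randomized, dosed subjects, and the synopsis summarizes sentinels separately.
- Minimum total: 27 + 17 + 17 = 61. Cohort 3 share: 17/61 = 27.9%.
- The original Section 9.1 prints 20 randomized for Cohort 3. That would give 20/(27 + 17 + 20) = 20/64 = 31.3%. The amendment corrects that number to 17, so 27.9% is used.

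**Cohorts 1 and 2**
- Eligibility accepts a measurement from 182.6 − 10 = 172.6 days before screening, while the AGV rule needs 182.6 days.
- A child whose earliest 111-901 measurement lies in that 10-day gap is eligible but has no baseline. A child with an earlier visit keeps a baseline over a longer interval.
- A Cohort 3 child who cannot start treatment before 6 months of age stays a further 3 months in pretreatment and then joins Cohort 2 (Section 9.1). If all of that time was spent in 111-206, the child has no 111-901 measurement.

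**Available data**
- Table 9.1.2 schedules anthropometry at Month 0 and 3 Months of the Cohort 3 observation period, and Table 9.1.1 schedules it again on Day 1. A workable interval exists.
- Its cost is precision. Annualizing multiplies the error in a length difference by 365.25/91.3 = 4.0 over 3 months, against 365.25/182.6 = 2.0 over 6 months.

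**The case against.** The strongest reply is that little depends on this. The primary efficacy endpoint is the length/height Z-score, which needs no earlier velocity. The secondary objective speaks of AGV over the 52 weeks, and all those intervals start on Day 1 and remain defined. Comparisons are labelled descriptive. The AGV formula is general, the infant measurements are scheduled, and further efficacy detail is left to the SAP. All of this stands, and it limits the severity. It does not remove the error: the protocol itself states the interval, and an SAP that supplied a workable Cohort 3 baseline would have to depart from it.

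A second reply is that Section 14.3 is visible only in the original protocol. The amended text at hand breaks off in Section 9.5.1. The summary of changes lists nothing for 14.3, and the amendment keeps both the Cohort 3 ages and the 3-month observation. Carry-over is therefore likely but cannot be confirmed.

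A reader might infer more than the documents support:
- That Cohort 3 velocity data are lost. They are not; only the start date is wrong.
- That results in Cohorts 1 and 2 turn on which of two baseline definitions is programmed. Section 14.3 otherwise refers to length as well as height, and standing height is measured only in children who can stand unsupported. The second sentence is best read as loose wording for the 6-month run-in. It conflicts with the interval and should be corrected, but it is not a rival analysis.
- That many Cohort 1 and 2 children fall in the 10-day gap. The protocol gives no basis for a count; it is an edge case of unknown size.
- That 20 of about 70 is the affected share. That adds sentinels, who are outside the efficacy population.

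**Conclusion.** The point holds for Cohort 3. Under Section 14.3 as supplied, change from baseline in AGV is undefined for the entire cohort, at least 17 of 61 randomized children (27.9%). The impossibility follows from the age limits alone. The percentage assumes minimum planned cohort sizes, and the whole point assumes that the amended Section 14.3 keeps the same interval. An additional but unknown number of Cohort 1 and 2 children could be affected through the 10-day gap or by moving up from Cohort 3. The primary endpoint and AGV on treatment are untouched. This is a should-fix for one secondary endpoint, not a threat to the trial's main efficacy result.

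**What to change.** Amend the wording of Section 14.3, or confirm that the amended version already does so:

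- **Cohort 3:** define baseline AGV from the first length of the observation period, whether taken in 111-901 or at Month 0 in 111-206, to Day 1. Note that a 3-month velocity is noisier than a 6-month one.
- **Cohorts 1 and 2:** keep the 111-901 start point, but allow the same 10-day shortfall that inclusion criterion 3 allows. For children who move from Cohort 3 to Cohort 2, accept measurements from the 111-206 observation period.
- **Standing-height sentence:** replace it with the same length/height definition, so that the section states one rule.

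Comparing Week 52 AGV directly in Cohort 3, adjusted for age and Day 1 length, would avoid relying on the noisy baseline. It is an optional modelling choice and is not needed to cure the error.

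The cost is text only: no new visits, measurements or subjects. The wording should be settled before the interim analysis. The price in Cohort 3 is a less precise baseline, and hence a less precise change in AGV, than in the older cohorts.

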14.2 Safety Analysis

The safety analysis will be performed on safety population as defined in Section 14.7.2 and will be considered descriptive.

All AEs will be coded using the most current version of MedDRA will be used by the Sponsor to assign system organ class and preferred term classification to events and diseases, based on the original terms entered on the CRF.

All AEs will be coded using MedDRA. The incidence of AEs will be summarized by system organ class, preferred term, relationship to study treatment (as assessed by investigator), and severity. All AEs, including SAEs and AEs that lead to permanent discontinuation from the study and from the study treatment, will be listed. Hypersensitivity reactions and

symptomatic hypotension are of interest, and the percentage of subjects who report these AEs will be presented. Hypersensitivity reactions will be defined in the SAP.

Clinical laboratory data will be summarized by the type of laboratory test. For each clinical laboratory test, descriptive statistics will be provided on baseline as well as all subsequent visits.

All other safety measures including laboratory tests, vital signs, ECG, echocardiogram, hip clinical assessment, and concomitant medication data will also be summarized descriptively. Data summaries will be presented by treatment group (when applicable) for each cohort and overall. All safety results will be listed.

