Efficacy will be assessed by change from baseline in AGV and length/height Z-score. Exploratory assessments will include change from baseline in growth parameters and body proportions by anthropometry. X-rays will be performed of the lower extremities and spine to evaluate for changes in bone morphology, quality, and growth. An MRI will be performed to assess the effect of BMN 111 on skull and brain morphology, including foramen magnum, ventricular and brain parenchymal dimensions. A board-certified, fellowship-trained (or equivalent) pediatric anesthesiologist will administer anesthesia during MRI measurements in the event that the subject is unable to remain still for the duration of the scan. Sleep studies will be conducted to evaluate sleep apnea. Additional assessments will be conducted to evaluate changes from baseline in bone metabolism and BMN111 pharmacodynamic biomarkers, and developmental/functional status.

NUMBER OF SUBJECTS PLANNED: Approximately 70 subjects, including at least 30 subjects in Cohort 1, at least 20 subjects in Cohort 2, and at least 20 subjects in Cohort 3.

NAME OF COMPANY BioMarin Pharmaceutical Inc. [name]	SUMMARY TABLE Referring to Part of the Dossier: Volume: Page:	FOR NATIONAL AUTHORITY USE ONLY:
NAME OF FINISHED PRODUCT: BMN 111		
NAME OF ACTIVE INGREDIENT: Modified rhCNP	Reference:	

DIAGNOSIS AND ALL CRITERIA FOR INCLUSION AND EXCLUSION:

Individuals eligible to participate in this study must meet all of the following criteria:

1. Diagnosis of ACH, confirmed by genetic testing. If subjects had previous genetic testing, subjects must have a lab report from a certified laboratory with the study specific mutation documented.
2. Age 0 to < 60 months, at study entry (Day 1)
3. Cohort 1 and 2 subjects must have at least a 6-month period of pretreatment growth assessment in Study 111-901 immediately before study entry and have one documented measurement of height/body length a minimum of 6 months (+/- 10 days) prior to the screening visit for 111-206. Cohort 3 subjects must have a minimum of 3 months of observation prior to treatment. This observational period can be obtained either (1) via prior enrollment in Study 111-901 or (2) via enrollment in this Study 111-206 for a minimum of 3 months of non-treatment observation prior to commencement of treatment.

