NAME OF COMPANY BioMarin Pharmaceutical Inc. [name]	SUMMARY TABLE Referring to Part of the Dossier: Volume: Page:	FOR NATIONAL AUTHORITY USE ONLY:
NAME OF FINISHED PRODUCT: BMN 111		
NAME OF ACTIVE INGREDIENT: Modified rhCNP	Reference:	

STATISTICAL METHODS:

Sample Size Determination: Approximately 70 subjects age 0 to < 60 months at study entry will participate in this study. No formal sample size calculations were performed. The number of subjects is considered appropriate to evaluate the safety and efficacy of BMN 111 in the target population.

Safety Analysis: All subjects who receive at least one dose of study treatment or who are randomized to the placebo-control group in this study will be included in the safety analysis. The safety analysis will be descriptive.

All AEs will be coded using the most current version of Medical Dictionary for Regulatory Activities (MedDRA) to assign system organ class and preferred term classification to event and disease, based on the original terms entered on the eCRF. The incidence of AEs will be summarized by system organ class, preferred term, relationship to study treatment as assessed by the investigator, seriousness, and severity. All AEs, including SAEs and AEs that lead to permanent discontinuation from the study and from the study treatment, will be listed.

All other safety measures including laboratory tests, vital signs, ECG, echocardiogram, hip clinical assessment, and concomitant medication data will also be summarized descriptively. Data summaries will be presented by treatment group (when applicable) for each cohort and overall. All safety results will be listed.

Efficacy Analysis:

All randomized subjects who receive at least one dose of study treatment or placebo in the study will be included in the efficacy analysis.

Efficacy variables, including AGV (based on length/height) and length/height Z-score according to normal reference standards (not ACH), along with their change from baseline will be summarized by treatment group and cohort. Comparisons between treatment groups by cohort on these variables will be carried out where appropriate. Statistical comparisons will be considered descriptive. 95% CIs will be provided along with p values for treatment group comparisons.

Sentinel subjects will be summarized apart for both efficacy and safety.

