9 INVESTIGATIONAL PLAN

9.1 Overall Study Design and Plan

This is a Phase 2 randomized, double-blind, placebo-controlled clinical trial of BMN 111 in infants and younger children with a diagnosis of ACH.

Subjects age \geq 6 months to $<$ 60 months old who have documented ACH confirmed by genetic testing; at least a 6-month period of pretreatment growth assessment in Study 111-901 immediately before study entry; and who meet the study eligibility criteria, will participate. Eligible subjects ranging from 0 months to $<$ 3 months old may enroll directly into 111-206 and have a minimum of 3 months of pre-treatment observation prior to commencing treatment with investigational product, or may enroll in 111-901 for a minimum of 3 months of pretreatment growth assessment immediately before roll-over to 111-206.

Approximately 70 subjects will be enrolled at approximately 10-15 clinical centers worldwide.

The primary objectives of this study are to assess the safety and tolerability of daily SC BMN 111 administered to infants and young children with ACH, and evaluate the effect of BMN 111 on Z-scores. Subjects will be enrolled into 3 age cohorts based on age at study screening starting with the eldest population. Within Cohorts 1 and 2, subjects will be stratified by age:

- Cohort 1 – children aged \geq 24 to $<$ 60 months (n \geq 30 total: 3 sentinel subjects who receive BMN 111, and at least 27 additional subjects randomized 1:1 to treatment or placebo control), stratified by age (\geq 24 to $<$ 36 months and \geq 36 months to $<$ 60 months)
- Cohort 2 – children aged \geq 6 to $<$ 24 months (n \geq 20 total: 3 sentinel subjects who receive BMN 111, and at least 17 additional subjects randomized 1:1 to treatment or placebo control), stratified by age (\geq 6 months to $<$ 15 months and \geq 15 months to $<$ 24 months)
- Cohort 3 – children aged 0 to $<$ 6 months (n \geq 20 total: 3 sentinel subjects who receive BMN 111, and at least 17 additional subjects randomized 1:1 to treatment or placebo control). Treatment begins at \geq 3 months to $<$ 6 months after 3 months of observation.

If subjects who enroll in Cohort 3 are not able to begin treatment by $<$ 6 months of age, they will continue in the pretreatment period for another 3 months before enrolling in Cohort 2 to fulfill the pretreatment requirement for Cohort 2.

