9.4.5 Method of Assigning Subjects to Treatment Groups

Subjects will be randomized in a 1:1 ratio, i.e., injection with placebo:15 µg/kg of BMN 111, using IXRS. An independent third-party vendor will develop the randomization schedule so that BioMarin and site personnel are blinded to treatment assignments. NOTE: In Japan, subjects are randomized separately within each cohort.

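### The protocol names only by-cohort efficacy comparisons for a study-wide primary objective; it should also name an overall comparison stratified by the randomization groups

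*Protocol*

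**What the plan says.** Section 8 makes change from baseline in length/height Z-score a primary objective for the whole study, without dividing it by cohort. Section 14.7.1 defines one efficacy population: all children randomized and dosed with blinded treatment.

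On the comparison itself, Section 14.3 says "Comparisons between treatment groups by cohort on these variables will be carried out where appropriate". It also has AGV summarized by treatment group and cohort, and Z-score in the same way. The efficacy paragraph of the amended synopsis carries the same sentence, calls the comparisons descriptive, and promises 95% confidence intervals with p values. Section 14.3 leaves further detail to the SAP.

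The safety text is worded differently. Section 14.2 says "Data summaries will be presented by treatment group (when applicable) for each cohort and overall", and the amended synopsis repeats it.

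On randomization, Section 9.1 gives "at least 27 additional subjects randomized 1:1 to treatment or placebo control" for Cohort 1 and "at least 17 additional subjects randomized 1:1 to treatment or placebo control" for each of Cohorts 2 and 3 (as amended). It adds that "Within Cohorts 1 and 2, subjects will be stratified by age". Section 9.4.5 as amended notes that "In Japan, subjects are randomized separately within each cohort". The synopsis plans "at least 30 subjects in Cohort 1, at least 20 subjects in Cohort 2, and at least 20 subjects in Cohort 3" and states that "No formal sample size calculations were performed". Sentinel subjects are summarized apart.

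**The concern.** The question is asked of all children in the study, but the comparison that the protocol names answers it three times, in groups as small as 8 against 9. No single between-arm estimate of the primary efficacy endpoint is named in advance. The contrast with the safety text makes this look like a choice of unit for efficacy, rather than a detail that happens to be missing.

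Three wide intervals, each with its own p value, can differ by chance, and the protocol does not say which result carries the conclusion. If an overall estimate were added only after the cohort results had been seen, the decision to combine them could be read as driven by those results. This matters for a study that calls itself descriptive too, because Section 14.1.1 plans an interim analysis to support marketing applications.

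**Working it through.** The plan gives no power, effect size or SD, so it has no precision figure to reproduce. Its counts do agree: 30 + 20 + 20 = 70 enrolled, less 3 × 3 = 9 sentinels, leaves 61 randomized, which is 27 + 17 + 17.

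**Inputs.** The randomized minimums are from Section 9.1 as amended. Split 1:1, they give 13 v 14 in Cohort 1 and 8 v 9 in each of Cohorts 2 and 3. Everything below is in units of the SD of the endpoint. The assumptions, none of them from the protocol, are a common SD, a common treatment effect and no dropout.

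**Within a cohort.** SE = √(1/n₁ + 1/n₂). The half-width of the 95% interval is t × SE on n₁ + n₂ − 2 degrees of freedom.
- Cohort 1: √(1/13 + 1/14) = 0.385; with 25 df, t = 2.06 and the half-width is 0.79.
- Cohorts 2 and 3, each: √(1/8 + 1/9) = 0.486; with 15 df, t = 2.13 and the half-width is 1.04.

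**Stratified by cohort.** Each cohort contributes information n₁n₂/(n₁ + n₂):
- Cohort 1: 182/27 = 6.74
- Cohorts 2 and 3: 72/17 = 4.24 each
- Sum: 15.21, so SE = 1/√15.21 = 0.256
- With 61 − 4 = 57 df, t = 2.00 and the half-width is 0.51.

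| Comparison | Per arm | SE (SD units) | 95% half-width | Width relative to stratified |
|---|---|---|---|---|
| Cohort 1 | 13 v 14 | 0.385 | 0.79 | 1.55 |
| Cohort 2 or 3 | 8 v 9 | 0.486 | 1.04 | 2.02 |
| All, stratified | 29 v 32 | 0.256 | 0.51 | 1 |

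The last row adds the smaller arms together (13 + 8 + 8). Which arm receives the odd child in each cohort does not change the SE.

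**Sensitivity.**
- Five strata (two age strata in each of Cohorts 1 and 2, plus Cohort 3), split as evenly as the counts allow, give SE 0.257. Stratifying by age costs almost nothing.
- Section 9.1 before the amendment had 20 additional children in Cohort 3. With 20, the stratified SE is 0.250, and the cohort SEs are 1.54, 1.94 and 1.79 times as large for Cohorts 1, 2 and 3. The picture does not change.

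Power is left out. It would need an assumed effect, and the plan states none.

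**The case against.** The strongest reply is that the protocol is silent on an overall comparison rather than opposed to it. The sentence does not say that by-cohort comparisons are the only ones. Section 14.3 sends further detail to a SAP that is not at hand, and the efficacy population spans all cohorts. This stands. A reader might infer that pooling is excluded, or that the comparisons will be unadjusted and will ignore the age strata and the separate randomization in Japan. The documents support neither inference: no model is given, so no adjustment is specified or ruled out. Section 14.3 is also available only as it stood before the amendment, because the supplied amended text stops within Section 9. The amended synopsis does, however, carry the same sentence.

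A second reply is that nothing is lost. The stratified estimate is the inverse-variance combination of the three cohort differences, so anyone with those differences and their intervals could form it. A reader might therefore go too far in saying that the primary question goes unanswered or that half the precision is thrown away. That is right. What is missing is an overall estimate named in advance.

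A third reply is that by-cohort reporting suits the design. Cohorts open in sequence, the dose may be set by age cohort, and pretreatment observation is shorter in Cohort 3. These are good reasons to keep the cohort results in view. They do not make them a sufficient answer to a study-wide objective. Under the amended Section 9.1, dose follows current age, so a child starting treatment in Cohort 3 at 3 months or older leaves that age band within about 3 of the 12 treatment months. Cohort is therefore not a pure dose group either.

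**Conclusion.** The point holds as a mismatch between question and comparison. The objective and the efficacy population are study-wide, and the protocol attaches confidence intervals and p values to comparisons that it names by cohort only, with no overall efficacy estimate named in the supplied text. That is a stated unit of comparison, not merely a detail deferred to the SAP.

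Its size is an interval about 1.5 times as wide in Cohort 1, and about twice as wide in Cohorts 2 and 3, as for a stratified comparison of all 61 randomized children. The ratios rest on the minimum cohort sizes, no dropout, and a common SD and effect from infancy to under 60 months. They would shift if variability or effect differed by age. Nothing in the plan is arithmetically wrong, and the comparisons are declared descriptive, so this is a worthwhile improvement rather than a flaw that invalidates the analysis.

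**What to change.** Amend the efficacy text in Section 14.3 and the synopsis to name, as the main descriptive estimate, one between-arm comparison of the change in Z-score at Week 52 over all randomized cohorts, and the same for AGV. It should be stratified by the randomization groups (cohort and age stratum), adjusted for the baseline value, and reported with its 95% confidence interval. Keep the by-cohort estimates beside it as supportive. Whether to add age, sex or Japan to the model is for the SAP.

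The cost is a few sentences, with no new data and no change to conduct. The small drawback is that the overall figure averages over age groups whose effect and dose may differ, which is why the cohort estimates should stay next to it.
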